## PROTOCOL SYNOPSIS

Title:	Phase I/II Trial of BMS-986205 and Nivolumab as First or Second Line Therapy in Hepatocellular Carcinoma
Protocol No.:	UCDC#276 (BMS ISR: CA017-084)
Phase of Development:	I/II
Investigational Product, Dose Regimen	BMS-986205 100mg daily (provided by BMS at no cost to subject) Nivolumab 240mg every 2 weeks (provided by BMS at no cost to subject)
Primary Objective:	1. To determine the safety and tolerability of BMS-986205 in combination with nivolumab in unresectable / metastatic HCC in the first or second line setting using CTCAE V5.0 criteria. 2. To determine efficacy as defined by objective response rate (ORR) of BMS-986205 in combination with nivolumab in unresectable / metastatic HCC in the first or second line setting using RECIST (version 1.1).
Secondary Objective(s):	1. To determine disease control rate (DCR), duration of response (DOR), progression free survival (PFS), and overall survival (OS) by RECIST 1.1 and ORR using immune RECIST (iRECIST) of BMS-986205 in combination with Nivolumab in unresectable HCC. 2. To further evaluate safety of BMS-986205 in combination with Nivolumab in unresectable HCC.
Correlative Objective(s):	1. To analyze serial blood samples for serum cytokine and tryptophan / kynurene levels, and to quantify the number, function, and gene expression of peripheral blood mononuclear cells (PBMCs). 2. To evaluate serial tumor tissue biopsies for tumor infiltrating immune cell subsets, expression of immune regulatory proteins including IDO1 and PD-L1, gene expression signatures, and mutational load. 3. To evaluate pre-treatment stool samples for microbiome signatures 4. To explore potential biomarkers.
Study Schema:	Phase I/II study with phase 1 being dose escalation of BMS-986205 with nivolumab and phase 2 being an open-label expansion in patients with HCC.
Study Population and Sample Size:	
 
Unresectable / metastatic HCC in the first or second line setting.
 
3-12 patients in the phase I (50mg or 100 mg daily of BMS-986205 and 240mg every two week of nivolumab)
 
17 patients in the phase II expansion cohort at MTD (either 50mg or 100mg daily of BMS-986205 and 240mg every two week of nivolumab) with the 6 patients accrued in the phase I at MTD counting towards the total.
 

Eligibility Criteria	Inclusion Criteria: 
 
Men and women <math>\geq 18</math> years of age at the time of study entry.
 
Willing and able to provide written informed consent for the trial.
 
Life expectancy <math>>12</math> weeks.
 
Histologically or imaging confirmed hepatocellular carcinoma (mixed hepatocellular/cholangiocarcinoma or fibrolamellar subtypes are excluded).
 
Have disease that is not amenable for curative treatment approach.
 

6. Have measurable disease based on RECIST v1.1.
7.  $\geq 1$  liver lesions accessible for core biopsy that was either not previously treated by liver-directed therapy or progressed following liver-directed therapy.
8. Child-Pugh score of A
9. ECOG performance status of 0 or 1.
10. Adequate hematology parameters:
  - a) Absolute neutrophil count (ANC)  $\geq 1000$  cell/mm^3
  - b) Platelet count  $\geq 50,000/\text{mm}^3$
  - c) Hemoglobin (Hgb)  $\geq 8$  g/dL
11. Acceptable blood chemistry levels:
  - a) AST/SGOT, ALT/SGPT  $\leq 5 \times$  upper limit of normal (ULN)
  - b) Total bilirubin  $\leq 2$  ULN
  - c) Creatinine  $\leq 2 \times$  ULN
12. Subjects with active hepatitis B virus (Hep B) are allowed if antiviral therapy for hepatitis B has been given for  $>8$  weeks and viral load is  $<100$  IU/ml prior to first dose of trial treatment. Subjects with untreated hepatitis C virus (HCV) are allowed.
13. Willingness to undergo mandatory pre-treatment biopsy (unless there is adequate archival tumor specimen available) and mandatory on-treatment biopsy.
14. Criterion modified per Amendment v4.0.
  - a. Women of child-bearing potential (WOCBP) must have a negative serum or urine pregnancy test (minimum sensitivity 25 IU/L or equivalent units of HCG) within 24 hr prior to planned treatment initiation.
  - b. Women of childbearing potential (WOCBP) must agree to follow instructions for method(s) of contraception (Appendix 9) for the duration of treatment with study treatment(s) plus 5 months post-treatment completion (i.e., 30 days [duration of ovulatory cycle] plus the time required for nivolumab to undergo approximately 5 half-lives).
  - c. Males who are sexually active with WOCBP must agree to follow instructions for method(s) of contraception for the duration of treatment with study treatment(s) plus 7 months post-treatment completion (i.e., 90 days [duration of sperm turnover] plus the time required for nivolumab to undergo approximately 5 half-lives). In addition, male participants must be willing to refrain from sperm donation during this time.
  - d. Males who are sexually active with WOCBP must agree to use a latex or synthetic condom during sexual activity (see Appendix 4) for the duration of treatment with study treatment plus 7 months after the last dose of the study treatment (i.e., 90 days [duration of sperm turnover] plus the time required for nivolumab to undergo approximately 5 half-lives). This criterion applies to azoospermic males as well.
  - e. Investigators shall counsel WOCBP, and male participants who are sexually active with WOCBP, on the importance of pregnancy prevention and the implications of an unexpected pregnancy. Investigators shall advise on the use of highly effective methods of contraception, which have a failure rate of  $< 1\%$  when used consistently and correctly. Hormonal contraceptives are not considered highly effective methods of contraception for participants receiving BMS-986205 in this study who are WOCBP.
15. Ability to adhere to the study visit schedule and other protocol requirements
16. Participants must be able to swallow pills intact.

**Exclusion Criteria:**

1. Received more than 1 prior systemic HCC-related therapy or currently receiving HCC-related systemic treatment or participating in a clinical trial and receiving study therapy.

2. Known history of positive test for human immunodeficiency virus (HIV) or known acquired immunodeficiency syndrome (AIDS).
3. Known diagnosis of immunodeficiency or active autoimmune disease or requiring systemic steroid equivalent of prednisone  $\geq 10$  mg/day or any immunosuppressive therapies  $\leq 7$  days of before the first dose of the study.
4. Active bacterial, viral (except Hepatitis B and C - see Inclusion Criterion 12), or fungal infection(s) requiring systemic therapy, defined as ongoing signs/symptoms related to the infection without improvement despite appropriate antibiotics, anti-viral therapy, anti-fungal therapy, and/or other treatment.
5. Active pneumonitis or history of interstitial lung disease (ILD) / pneumonitis requiring steroids.
6. Clinically significant ascites.
7. Hepatic encephalopathy.
8. Any significant medical condition including additional malignancies, laboratory abnormalities, or psychiatric illness that would prevent the subject from participating and adhering to study related procedures.
9. Live attenuated vaccine  $\leq 30$  days before the first dose of study treatment. Examples of live vaccines include, but are not limited to, the following: measles, mumps, rubella, chicken pox, yellow fever, rabies, *Bacillus Calmette-Guérin* (BCG), and typhoid vaccine. Seasonal influenza vaccines for injection are generally killed virus vaccines and are allowed; however, intranasal influenza vaccines (e.g., FluMist®) are live attenuated vaccines and are not allowed.
10. Use of strong inhibitor / inducer of CYP3A4 or CYP1A2.
11. Known history of surgery or medical condition that may affect drug absorption, per investigator discretion.
12. Participants with a history of G6PD deficiency or other congenital or autoimmune hemolytic disorders. All participants will be screened for G6PD deficiency prior to enrollment using quantitative or qualitative G6PD assay results to suggest underlying G6PD deficiency.
13. Participants with a personal or family (i.e., in a first-degree relative) history or presence of cytochrome b5 reductase deficiency (previously called methemoglobin reductase deficiency) or other diseases that puts them at risk of methemoglobinemia. All participants will be screened for methemoglobin levels prior to enrollment using blood methemoglobin  $>$  ULN, assessed in an arterial or venous blood sample or by cooximetry.
14. Subjects with screening QTc interval  $> 480$  ms.
15. Liver directed therapy  $\leq 4$  weeks before the first dose of study.
16. History of esophageal or gastric variceal bleeding within 3 months of study enrollment.
17. Treatment with botanical preparations (e.g., herbal supplements or traditional Chinese medicines) intended for general health support or to treat the disease under study within 2 weeks prior to enrollment.
18. Prior history of serotonin syndrome.
19. Prior treatment with BMS-986205 or any other IDO1 inhibitors.
20. Women who are breastfeeding.
21. History or presence of hypersensitivity or idiosyncratic reaction to methylene blue.
22. History of allergy or hypersensitivity to any study treatment components, specifically to that of BMS-986205.

[figure not shown]
	
 
23. Participants who have had major surgery requiring general anesthesia or significant trauma who have not recovered per physician determination for at least 14 days prior to enrollment.
 
24. Participants who have had major surgery requiring general anesthesia or significant trauma who have not recovered per physician determination for at least 14 days prior to enrollment.
 
25. Participants with uncontrolled adrenal insufficiency.
 

Endpoints:	
Phase I:
 
 
• Safety profile of BMS-986205 in combination with nivolumab in unresectable HCC using CTCAE V5.0 criteria
 
 
Phase II:
 
 
• Safety profile of BMS-986205 in combination with nivolumab in unresectable HCC using CTCAE V5.0 criteria
 
• ORR of BMS-986205 in combination with nivolumab in unresectable HCC using RECIST 1.1 criteria.
 
 
Secondary Endpoints
 
 
• DCR which include CR, PR and SD from the first report of SD or better until progression by RECIST 1.1
 
• DOR defined by the first report of SD or better until progression by RECIST 1.1
 
• ORR using immune RECIST (iRECIST)
 
• PFS defined by date of enrollment until the first date of documented disease progression or death by RECIST 1.1
 
• OS defined by date of enrollment until death from any cause by RECIST 1.1.
 
• Correlation of PD-1/L1 expression (+/-) and IDO1 expression (+/-) at: 1) baseline, 2) on treatment, and 3) progression, with ORR, PFS and OS.
 

Statistical Considerations	
This is a phase I/II study using a Simon optimal two-stage design for efficacy of BMS-986205 in combination with nivolumab. In the phase I portion, we will treat patients following 3+3 standard design with dose escalation in BMS-986205 along with fixed dose of nivolumab. BMS-986205 dose level 1 will be 50mg and dose level 2 will be 100mg. 3 patients will be treated with BMS-986205 at dose level 1 of 50mg along with fixed dose of nivolumab. If no patient experiences a DLT at dose level 1, we will add 3 patients will be treated at a dose of 100 mg of BMS-986205 with fixed dose of nivolumab. If 1 of 3 patients has a DLT at DL1, we will add 3 patients at a dose of 50 mg. If <math>\leq 1</math> of 6 patients has a DLT at 50mg of BMS-986205, 3 patients will be treated at 100mg. Maximum tolerated dose will be defined as <math>\leq 1</math> of 6 patients at DL1 or DL2 experiencing a DLT. After identifying the MTD, the phase II expansion phase will be initiated with 3 additional patients at the MTD. A maximum total of 17 patients at MTD will be treated on trial including 6 patients treated during phase I portion at MTD. An interim efficacy analysis will be done after 9 patients (including the 6 patients in phase I portion) have been treated. If at least 1 patient out of the 9 initial patients treated at MTD achieves a response, we will accrue 8 more patients at the MTD. If at least 3 of the 17 patients treated at MTD achieve a response, we will deem the treatment worthy of further study, provided the safety profile is acceptable.
 
The Simon optimal two stage design described above provides 80% power to detect the difference between an acceptable response rate of 25% vs. an unacceptable rate of 5% at the 0.05 level (1-sided). The estimated time to accrue 20-23 patients is 18 months, at approximately 1.1 patients per month. The ORR will be estimated as the proportion of participants who experience an objective response, along with its exact 95% confidence

	interval; the disease control rate will be analyzed similarly. DOR, PFS, and OS will be analyzed using Kaplan-Meier methods; medians and 95% confidence intervals will be computed. DLTs, adverse events, serious adverse events, and clinical laboratory values outside normal limits will be listed for each patient and summarized by body system and dose level in frequency tables.
Estimated Accrual Period:	24 months
Estimated Duration of Participation:	30 months to complete study assessments
Estimated Study Duration:	36 months
Correlatives:	
Tissue - Multi-plex IHC/IF for PD-L1, IDO, CD3, FOXP3 and other markers of interest. Immune related gene expression analysis. Flow cytometry of fresh tumor core to analyze TME with focus on T-cell and dendritic cell activation/functional markers. TCR deep sequencing to evaluate T cell clonal diversity and proliferation.
 
PBMCs - Flow cytometry to determine peripheral immune phenotype. Ex-vivo analysis of PD-1+ T-cells for proliferative and cytokine production activity and metabolic analysis using the Seahorse platform. TCR deep sequencing to evaluate T cell clonal diversity and proliferation.
 
Plasma - Cytokine analysis by Luminex. Tryptophan and Kynurene levels.
 
Stool – Microbiome Analysis

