In particular, the CA017-003 Phase 1/2a study reported that the maximum tolerated dose of BMS-986205 was 200 mg when combined with nivolumab, [24]. Anti-tumor activity was found during the dose expansion phase of BMS-986205 100mg among a group of heavily pre-treated bladder (25 patients) and cervical cancer patients (22 patients). In the bladder group, the objective response rate (ORR) was 32 percent (8/ 25 patients) and the disease control rate (DCR) was 44 percent (11/25 patients). In the cervical cancer cohort, ORR was 14 percent (3/ 22 patients) and DCR was 64 percent (14/22 patients). Patients with more than 1% of PD-L1 had ORR of 46% and 25% in bladder and cervical cancer respectively. The combination regimen was well tolerated with only 4 patients (1.4%) discontinuing from the study due to the drug toxicity. The most commonly reported adverse effect of any grade were fatigue (13.6%), nausea (11.5%), and decreased appetite (10.5%).

Given the success of immune checkpoint blockade in HCC, the existing data for synergistic effects with IDO inhibition and the known expression of IDO in HCC, we propose a phase I/IIa evaluating the safety and demonstrating the efficacy of BMS-986205 + nivolumab in unresectable HCC.

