### 3.0 STUDY DESIGN

This is a phase I/II study using a Simon optimal two stage design for efficacy of BMS-986205 in combination with nivolumab as illustrated in the schema. For the phase I portion the primary endpoint is to determine safety profile of BMS-986205 in two dose levels with nivolumab in unresectable HCC using CTCAE V5.0 criteria. For the phase II portion the primary endpoints are safety and toxicity and the objective response rate using the using RECIST criteria. Exploratory endpoints include disease control rate (DCR), duration of response (DOR), ORR using iRECIST, progression free survival (PFS), overall survival (OS), and correlative studies.

For phase I dose escalation, up to two dose levels of BMS-986205 will be evaluated: 50 mg daily and 100mg daily. These two dose levels were selected based on the clinical data described above. We have chosen 50 mg daily as the starting dose level given the existing safety data for this dose and the safe use of this dose in use with other immunotherapy combinations. The dose of BMS-986205 will be escalated to 100 mg daily if 0 of the first 3 patients experience a dose limiting toxicity (DLT) at 50 mg BMS-986205. Three additional patients will be added to receive 50 mg BMS-986205 if 1 of the first 3 patients experiences a DLT. The dose of BMS-986205 will be escalated to 100 mg daily if no more than one of six patients experience a DLT at 50 mg BMS-986205. The expansion phase will be conducted after MTD is reached, which will be defined as no more than one of six patients develops a DLT at 50 mg or 100 mg of BMS-986205 daily with nivolumab. If BMS-986205 50mg daily is not tolerated the study will be halted and modified after discussion with the principal investigator (PI) and BMS. The 6 patients at the maximum tolerated dose in the phase I portion treated at MTD will count towards the 17 patients needed in the phase II expansion cohort. The phase II cohort will be run as a Simon two-stage design to allow for early trial stoppage for futility. We designate an ORR as defined by RECIST criteria of 5% as not worthy of further investigation and of 25% as worthy of further investigation. In the first stage 9 patients will be accrued and at least 1 response must be observed within 6 months of treatment (or longer at PI discretion) to continue the trial (n1=9, r1=0) (see study schema). BMS-986205 will be administered orally daily and nivolumab will be administered intravenously until disease progression.

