### 11.5 Efficacy

Response and progression will be evaluated in this study using the new international criteria proposed by the revised Response Evaluation Criteria in Solid Tumors (RECIST) guideline (version 1.1) [35] as well as iRECIST criteria. Changes in the largest diameter (unidimensional measurement) of the tumor lesions is used in the RECIST criteria. Radiologic assessment is to be repeated at the following time points (+/- 7 days): at the end of 8 and 16 weeks, then every 12 weeks, and at End of Treatment. Patients that go off treatment without radiological progression will have scans repeated every 3 months until documented disease progression or start of new therapy.

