#### **11.5.3.4 Duration of Overall Response**

The duration of overall response is measured from the time measurement criteria are met for CR or PR (whichever status is recorded first) until the first date that recurrence or PD is objectively documented, taking as reference for PD the smallest measurements recorded since the treatment started.

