#### **11.5.3.5 Duration of Stable Disease**

SD is measured from the start of the treatment until the criteria for disease progression are met, taking as reference the smallest measurements recorded since the treatment started. The clinical relevance of the duration of SD varies for different tumor types and grades. Therefore, it is highly recommended that the protocol specify the minimal time interval required between two measurements for determination of SD. This time interval should take into account the expected clinical benefit that such a status may bring to the population under study.

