### 14.3 Evaluation of Efficacy

The ORR will be estimated as the proportion of participants who experience an objective response, along with its exact 95% confidence interval; the disease control rate will be analyzed similarly. DOR, PFS, and OS will be analyzed using Kaplan-Meier methods; medians and 95% confidence intervals will be computed.

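### The synopsis starts duration of response at the first SD or better, Section 11.5.3.4 starts it at the first CR or PR, and Section 14.3 does not say which one the Kaplan-Meier analysis uses

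*Combined protocol and SAP*

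**What the plan says.** **Protocol Synopsis, Endpoints.** Among the secondary endpoints: "DOR defined by the first report of SD or better until progression by RECIST 1.1". The DCR line in the same list uses nearly the same phrase: "DCR which include CR, PR and SD from the first report of SD or better until progression by RECIST 1.1".

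**Section 11.5.3.4.** "The duration of overall response is measured from the time measurement criteria are met for CR or PR", whichever is recorded first. The interval ends when recurrence or PD is objectively documented.

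**Section 11.5.3.5.** Stable disease has a separate duration with a third starting point: "SD is measured from the start of the treatment until the criteria for disease progression are met".

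**Section 11.5.3.6.** Only PR and CR count towards the objective response rate.

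**Section 14.3**, and the same text under Statistical Considerations in the synopsis: "DOR, PFS, and OS will be analyzed using Kaplan-Meier methods", with medians and 95% confidence intervals. No start event, analysis set or cross-reference is given. Section 2.2 names DOR as a secondary objective without defining it, and Section 14.1, although headed as an overview of endpoints, does not mention it.

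**Section 3.0** gives DOR a lower status: "Exploratory endpoints include disease control rate (DCR), duration of response (DOR".

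**Section 11.5** sets the scans "at the end of 8 and 16 weeks, then every 12 weeks, and at End of Treatment".

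**The concern.** The two definitions differ in when the clock starts and in who is analysed. Under Section 11.5.3.4 a patient whose best result is SD has no DOR. Under the synopsis that patient contributes an interval, and a late responder is credited with the SD time that came before the response. The synopsis quantity is therefore a duration of disease control. It is not the protocol's duration of SD either, because that runs from the start of treatment.

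No precedence rule was found in the documents, and Section 14.3 points to neither definition. Two analysts working from the same text could report DOR in different patients, from different dates and with different medians. With so few responders expected, a handful of added SD patients could change the reported figure, and the choice should not be made after the data are seen.

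**Working it through.** **1. The plan's own design figure, to show what is not affected.** Inputs from Sections 3.0, 14.1 and 14.2: first stage of 9 patients, continue with at least 1 response; 17 in total, success with at least 3 responses; response rates 5% and 25%; one-sided 0.05; 80% power.

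P(success | p) = Σ over x ≥ 1 of Bin(x; 9, p) × P[Bin(8, p) ≥ max(0, 3 − x)]

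- p = 0.05: 0.0466, within the 0.05 ceiling
- p = 0.25: 0.812, against a stated 80%

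The ORR design reproduces. It uses responses only, so the DOR definition does not enter it. The documents state no figure for DOR.

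**2. The two definitions side by side.**

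| | Synopsis | Section 11.5.3.4 |
|---|---|---|
| Start | first SD, PR or CR | first PR or CR |
| Who enters | anyone with SD or better | responders only |
| End | progression by RECIST 1.1 | documented recurrence or PD |

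**3. Size for one patient.** Section 11.5 puts scans at weeks 8 and 16, then 16 + 12 = 28 and 28 + 12 = 40.

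- SD at week 8, first PR at week 16: the synopsis starts 16 − 8 = 8 weeks earlier.
- SD at week 8, first PR at week 28: 28 − 8 = 20 weeks earlier.
- SD at week 8, never a response, PD at week 16 or 28: the synopsis gives 8 or 20 weeks; Section 11.5.3.4 gives no DOR.

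**4. Direction of the median.** Two invented sets, without censoring, to show direction only:

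- Three responders, each with SD at week 8, PR at week 16 and PD at week 40. Section 11.5.3.4 gives 40 − 16 = 24 weeks each; the synopsis gives 40 − 8 = 32. The median rises from 24 to 32.
- Three responders with PR at week 8 and PD at week 40 (32 weeks under either rule), plus four never-responders with SD at week 8 and PD at week 16 (8 weeks, synopsis only). Under the synopsis the survival estimate after week 8 is 3/7 = 0.43, below one half. The median falls from 32 to 8.

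**5. How many responders carry the 11.5.3.4 analysis.** With 17 treated: 17 × 0.25 = 4.25 expected at the 25% rate and 17 × 0.05 = 0.85 at the 5% rate. Full enrolment also implies at least one response among the first 9. P(none in 9) at 25% is 0.75^9 = 0.0751, so the conditional expectation is (4.25 − 0.0751 × 8 × 0.25) / (1 − 0.0751) = 4.43. Either way it is about 4.

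**6. What Section 11.5.3.4 leaves open.** Section 11.5.3.3 reports both a response rate and a confirmed response rate, and nothing says which responders enter DOR. Section 11.5.3.4 ends DOR at recurrence or PD and is silent on death, whereas PFS in Section 11.5.3.8 counts death as an event. Aligning the start date alone would still leave two analysts free to differ.

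**The case against.** The best defence is that this is a drafting slip with an obvious answer. The synopsis DOR line repeats the phrase of the DCR line directly above it, which looks like carry-over. The body of the protocol is clear about what a response is and gives SD its own duration, so an experienced analyst would follow Section 11.5.3.4. DOR drives no decision. Most of this stands, and it limits the importance of the point. It does not remove it: the line is current text in the endpoint list, no precedence rule was found, and Section 14.3 does not direct the analyst to the body definition.

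Three stronger readings are tempting but not supported.

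- **That the synopsis rule makes DOR look longer.** It lengthens the interval of a late responder but also admits short SD intervals. Step 4 shows the median moving in both directions.
- **That the distortion can be sized from the earlier bladder and cervical cohorts in Sections 1.3 and 1.5.** Those patients did not have HCC, and the response counts include unconfirmed responses: 7 of 8 and 1 of 3 were confirmed. Scaling them to 17 HCC patients adds no evidence.
- **That the response rules also put primary ORR at risk, because Table 2 has no column for non-target lesions.** RECIST 1.1 is adopted by name, and Section 11.5.3.1 is headed as covering target lesions only. Section 11.5.3.2 counts best response only up to progression, and Appendix 12 rules out a RECIST 1.1 response after progression. Treatment beyond first progression under Section 6.1.1 relies on iRECIST for managing patients, not for defining RECIST 1.1 response. What remains is an incomplete table whose intended rule can be inferred, with no demonstrated effect on ORR.

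**Conclusion.** The contradiction is real and should be corrected. As written, the synopsis defines a duration of disease control under the name of duration of response, and the analysis section does not choose between the two definitions. For an individual responder the start date can differ by 8 or 20 weeks on the first three planned scans, and patients with SD but no response move in or out of the analysis set. The net effect on the median has no predictable sign, and the documents do not allow it to be estimated for this population.

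These sizes assume scans on schedule and SD at week 8. The consequence is limited to an endpoint that is secondary in the synopsis and exploratory in Section 3.0. The rules of at least 1 response in 9 and at least 3 in 17, and the design's error rate and power, do not depend on it. The DCR line in the synopsis is an editorial matter: Sections 11.5.3.7 and 14.3 already treat DCR as a proportion.

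**What to change.** - **Synopsis, DOR line:** replace it with the Section 11.5.3.4 definition: responders only, from the first CR or PR until documented recurrence or PD.
- **Synopsis, DCR line:** word it as the proportion in Section 11.5.3.7.
- **Section 14.3**, and the matching synopsis paragraph: refer to 11.5.3.4 for DOR and 11.5.3.7 for DCR. State whether DOR includes all responders or only confirmed responders, and whether a death without documented PD is an event or is censored, and at what date.
- **Optional, editorial:** add non-target status to Table 2, in line with RECIST 1.1 and Appendix 12.

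The core cost is two synopsis lines and a few sentences in Section 14.3. No extra scans, patients or change to the sample size are needed. The drawback is precision: median DOR would rest on about 4 responders at a 25% response rate, and fewer if only confirmed responses count, so its interval will be wide. Listing each responder's duration beside the Kaplan-Meier estimate would make that plain.
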